## 4.5 Safety Monitoring Committee

An SMC consisting of Sponsor representatives as well as members independent from the Sponsor will be established. The membership should include at least 1 Sponsor representative, 1 member independent from the Sponsor, and 1 rheumatologist. The SMC will review and evaluate the blinded interim safety data after the final subject of each cohort has been evaluated at the Day 43 visit. Initiation of enrollment at the next dose level will only commence after endorsement of the SMC and Sponsor. In addition, the SMC will review neurological AEs and other safety events during the study as considered necessary. When available from each full cohort, the SMC will review all Day 85 safety data and may recommend that an already enrolled succeeding dose cohort be discontinued, or its treatment regimen truncated.

The SMC will be responsible for making recommendations as to whether it is scientifically and ethically appropriate to continue enrollment, discontinue treatment groups, or discontinue the study. Only the SMC is authorized to evaluate unblinded interim efficacy and safety analyses prior to the completion of each dosing cohort, if appropriate. Study sites will receive information about interim results ONLY if they need to know for the safety of their subjects.

Details of the SMC and interim analyses will be documented in an SMC charter and SMC analysis plan. All Investigators and subjects will remain blinded to the original treatment assignments before final database lock.

## 5.0 STUDY TREATMENTS

### 5.1 Treatments Administered

Eligible subjects will receive 4 doses of either brentuximab vedotin 0.3, 0.6, 1.2, or 1.8 mg/kg IV or matching placebo, given every 3 weeks (Days 1, 22, 43, and 64) during the treatment period.

Individual doses are based on subject weight (see Section 5.5) and will be administered as an IV infusion over approximately 30 minutes. The study drug cannot be mixed with other medications.

Dose reductions are not permitted; however, dosing will be withheld if a subject experiences Grade 2 neuropathy. Resumption of dosing will be decided on a case-by-case basis by the Medical Monitor. Subjects who experience Grade 3 or higher neuropathy or who miss more than a single dose will be withdrawn from the study (see Section 4.4.4).

Further instructions on the dose preparation and administration will be provided in the Pharmacy Manual.

### 5.2 Identity of Investigational Product

Study drug will be provided by the Sponsor in individual kits containing four 50-mg vials. Each vial of active study drug contains 55 mg for injection (brentuximab vedotin), trehalose, sodium citrate, and polysorbate 80. The 5-mg overfill in each vial is to ensure that the labeled quantity of 50 mg may be withdrawn. Vials containing placebo are identical in appearance. The vials will be reconstituted with the appropriate amount of Sterile Water for Injection. The pH of reconstituted product is approximately 6.6. Vials and reconstituted study drug should be stored at 2° to 8°C. Brentuximab vedotin does not contain preservatives; therefore, opened and reconstituted vials of brentuximab vedotin should be used as soon as possible. If not used immediately, the in-use storage should not be longer than 24 hours. It is recommended that brentuximab vedotin vials and solutions be protected from direct sunlight until time of use. Reconstituted vials and solutions must not be shaken.

Additional information on the storage, handling, and destruction of study drug will be provided in the Pharmacy Manual.

### **5.3 Method of Assigning Subjects to Treatment Group**

Once the subject meets inclusion and exclusion criteria and has provided written informed consent, the study site will request the study medication assignment using the Interactive Web Response System (IWRS).

A total of 10 subjects in each dose cohort will be randomly assigned in a 4:1 ratio, resulting in 8 subjects assigned to each of the 4 brentuximab vedotin dose cohorts and a total of 8 subjects assigned to placebo (2 per cohort).

To randomly assign a subject to treatment, the study site will use the internet to access the IWRS. Subjects will be assigned their 6-digit subject number, starting with a 3-digit site number followed by a hyphen and a 3-digit sequential number (eg, 101-001). The IWRS will provide the study drug kit number(s) of the blinded study drug to be dispensed.

### **5.4 Selection of Doses in the Study**

The doses selected for administration in this study are at or below those used for the standard regimen of brentuximab vedotin when given for HL and ALCL. See Section [2.5](#) for additional discussion of the dose selection.

### **5.5 Selection and Timing of Dose for Each Subject**

Dosing is based on subject weight at baseline; however, doses will be adjusted for subjects who experience a  $\geq 10\%$  change in weight from baseline. Actual weights will be used except for subjects weighing  $> 100$  kg; the dose for these subjects will be calculated based on 100 kg. Rounding is permissible within 5% of the nominal dose.

Subjects will receive 4 doses of study drug (either brentuximab vedotin or placebo according to the randomized treatment) given 3 weeks apart during the treatment period (Days 1, 22, 43, and 64).

### **5.6 Blinding**

This is a randomized, double-blind, placebo-controlled study with limited access to the randomization code. Brentuximab vedotin and placebo solutions for IV administration will be identical in physical appearance. The treatment each subject will receive during the treatment period will not be disclosed to the Investigator, study site personnel, subject, Sponsor, or Quintiles. Upon request, treatment assignments will be revealed to the Investigators when the clinical study report is final. The SMC will review and evaluate blinded interim safety data after the final subject of each cohort has been evaluated at the

Day 43 visit. The data for a given cohort may be unblinded for preliminary data analyses after completion of all subjects for the cohort (Day 85 and/or Day 127).

The process for breaking the blind will be handled through the IWRS. Investigators are strongly discouraged from requesting the blind be broken for an individual subject, unless there is a subject safety issue that requires unblinding and would change subject management. Any site that breaks the blind under inappropriate circumstances may be asked to discontinue its participation in the study. If the blind is broken, it may be broken for only the subject in question and the subject must be withdrawn from the study.

The Sponsor and Quintiles must be notified immediately if a subject and/or Investigator is unblinded during the course of the study. Pertinent information regarding the circumstances of unblinding of a subject's treatment code must be documented in the subject's source documents and case report forms (CRFs).

## **5.7 Prior and Concomitant Treatments**

A concomitant treatment is any drug or substance administered from the time of the subject's written informed consent until the subject's last study visit, including over-the-counter medications, herbal medications, vitamins, NSAIDS, and mineral supplements. The use of all concomitant treatments during the study, including the start and stop dates, must be recorded on the subject's CRF, according to instructions for CRF completion.

If there are changes to a concomitant medication or if the subject requires concomitant therapy for an AE, it must be reported on the appropriate CRF page and in the source medical records.

Previously failed or intolerated treatments for SLE will be recorded in the subject's CRF as a prior medication.

### **5.7.1 Excluded Medications**

Treatment with any of the following within the timeframes indicated before baseline (if not otherwise previously dosed longer term according to Section 5.7.2) are not allowed:

- colchicine or corticosteroids: 2 weeks;
- cyclosporin, tacrolimus, methotrexate, leflunomide, azathioprine, 6-mercaptopurine, cyclophosphamide, tofacitinib, or other JAK inhibitors: 4 weeks;
- biologic therapies, including belimumab, abatacept, IL-6, and TNF- $\alpha$  (eg, infliximab, adalimumab, certolizumab pegol, or golimumab) antagonists: 8 weeks;

- rituximab or other B cell depleting therapies: 6 months (subjects who have been exposed to B cell depleting therapies must have a normal peripheral B cell count at baseline, if not demonstrated before);
- other drugs or biologics, including investigational products: 8 weeks or 5 half-lives, whichever is longer;
- antibiotics: 2 weeks; or
- live vaccinations: 8 weeks.

Concomitant use of brentuximab vedotin and bleomycin is contraindicated due to pulmonary toxicity (see [Appendix 4](#)); therefore, the administration of bleomycin is not allowed during this study.

### **5.7.2      Allowed Medications**

If taking the following medications, the subject must be on a stable dose prior to the baseline visit for at least the durations indicated and be willing and able to continue at stable doses throughout the study:

- corticosteroids (up to 40 mg/day prednisone or equivalent): 4 weeks;
- hydroxychloroquine or other antimalarials: 3 months;
- mycophenolate mofetil, mycophenolic acid, azathioprine, methotrexate, leflunomide, or 6-mercaptopurine: 3 months;
- NSAIDS and COX-2 inhibitors at or below the maximum approved dose: 2 weeks; or
- Oral, injected, or implanted hormonal methods of contraception, as well as HRT: 3 months.

Temporary increases in corticosteroid dosage (“bursts”) are permissible during the study as follows.

- The maximum duration of a burst is limited to 14 days duration on no more than 2 occasions.
- The corticosteroid dose must return to the preburst dose or lower at least 1 week before the 12-week assessments.
- The maximum dosage during a burst is up to 0.5 mg/kg prednisone, or equivalent, including any other steroids being given.

- The specific dose and taper schedule is at the discretion of the Investigator.

No increases in corticosteroid dosage outside of bursts are permitted. Decreases in the maintenance corticosteroid dose are allowed.

MMAE is primarily metabolized by cytochrome P450 enzyme 3A4 (CYP3A4), and is a substrate of P-glycoprotein (P-gp). Caution should be used in co-administering drugs which strongly inhibit CYP3A4 or P-gp, since increased MMAE exposures may result.

### **Required Premedication and Postmedication**

Medication should not be administered for the prevention of infusion-related reactions prior to the first dose of brentuximab vedotin. However, subjects who experience a Grade 1 or Grade 2 infusion-related reaction may receive subsequent brentuximab vedotin infusions with premedication as described in Section 6.3.2.

## **5.8 Treatment Compliance**

All doses of study drug (including placebo) will be administered in the clinic under the supervision of the Investigator or designee and recorded in the CRFs. Therefore, no assessment of treatment compliance is planned.

The prescribed dosage, timing, and mode of administration may not be changed. Any departures from the intended regimen must be recorded in the CRFs.

## **5.9 Study Drug Accountability**

The Investigator, a member of the study site staff, or a hospital pharmacist must maintain an adequate record of the receipt and distribution of all study drug using the Drug Accountability Form. These forms must be available for inspection at any time.

## 6.0 EFFICACY, SAFETY, PHARMACOKINETICS, AND PHARMACODYNAMICS

### 6.1 Schedule of Events

A schedule of events is presented in [Table 3](#).

### 6.2 Efficacy Measures

#### 6.2.1 Response Assessments

The following response assessments will be performed at the time points indicated in the schedule of events ([Table 3](#)):

- BILAG 2004;
- SLEDAI-2K;
- CLASI;
- SJC – 66 joints;
- TJC – 68 joints;
- PtGP;
- PtGA;
- PhGA;
- HAQ-DI;
- SF-36;
- FACIT-F;
- LupusQoL; and
- high-sensitivity C-reactive protein (hsCRP) and erythrocyte sedimentation rate (ESR).

Details of these scales and assessments will be provided in the study reference manual.

## 6.2.2 Response Definitions

The following definitions will be used to evaluate the response assessments.

- **BILAG Clinical Response** is defined as (must meet both criteria):
  - BILAG C scores or better in all organ domains; and
  - no new BILAG A or B scores in any organ domain.
- **Systemic Lupus Erythematosus Responder Index (SRI)** definition of response includes:
  - reduction in Safety of Estrogens in Lupus Erythematosus National Assessment (SELENA)-SLEDAI of at least 4 points;
  - no new BILAG A organ domain scores and no more than 1 new BILAG B score; and
  - no worsening (increase of < 0.3) in PhGA versus baseline.
- **BILAG-based Combined Lupus Assessment (BICLA)** definition of response includes:
  - BILAG-2004 improvement (all A scores at baseline improved to B/C/D, and all B scores improved to C or D);
  - no worsening in disease activity (no new BILAG-2004 A scores and  $\leq$  1 new B score);
  - no worsening of total SLEDAI-2K score from baseline;
  - no significant deterioration (< 10% worsening) in 100 mm visual analogue PhGA; and
  - no treatment failure (defined as nonprotocol treatment [ie, new or increased immunosuppressives or antimalarials or increased or parenteral corticosteroids] or premature discontinuation from study treatment).
- **Active renal disease** is defined as either:
  - both of urinary protein:creatinine ratio  $\geq$  0.5 and active urinary sediment as defined by at least one of the following (in the absence of urinary tract infection):
    - more than 5 red blood cells (RBCs)/high power field (hpf) (or above the reference range for the laboratory),

- more than 5 white blood cells (WBCs)/hpf (or above the reference range for the laboratory), or
- presence of cellular casts (RBC or WBC); or
- isolated severe proteinuria without active sediment (eg,  $\geq 3.5$  grams/day or equivalent).
- **SELENA SLE flare** definitions include:
  - SELENA mild/moderate flare:
    - a change in SLEDAI  $\geq 3$  points,
    - new/worse skin, stomatitis, serositis, arthritis, or fever,
    - increased prednisone  $< 0.5$  mg/kg/day,
    - added NSAID/hydroxychloroquine, or
    - $\geq 1.0$  increase in PhGA (on a 0 to 3 scale);
  - SELENA severe flare:
    - change in SLEDAI  $> 12$ ,
    - new/worse CNS-SLE, vasculitis, nephritis, myositis, platelet count  $< 60,000/\mu\text{L}$ , hemolytic anemia with hemoglobin  $< 7$  mg/dL, requiring doubling or  $> 0.5$  mg/kg/day prednisone,
    - hospitalization for SLE,
    - prednisone  $> 0.5$  mg/kg/day,
    - new immunosuppressive, or
    - increased PhGA to  $> 2.5$ .
- **BILAG SLE flare** definitions include:
  - BILAG flare:
    - development of any new BILAG A domain score, or
    - $\geq 2$  new BILAG B domain scores;
  - BILAG severe flare: development of any new BILAG A domain score.

- **Renal flare** is defined as any of these 3 events:
  - increased proteinuria, as defined by:
    - a urinary protein:creatinine ratio  $> 0.5$ , provided the 24-hour urine protein (if done) contains a total of at least 500 mg of protein, OR
    - a reproducible increase in 24-hour urine protein levels to:
      - $> 1,000$  mg if the baseline value was  $< 200$  mg,
      - $> 2,000$  mg if the baseline value was between 200 and 1,000 mg, or
      - more than twice the value at baseline if the baseline value was  $> 1,000$ ;
  - impaired renal function, as defined by a reproducible decrease in eGFR of  $> 20\%$ , accompanied by proteinuria ( $> 1,000$  mg/24 hours), hematuria ( $\geq 4$  RBCs/hpf or above the reference range for the laboratory), and/or cellular (RBC and WBC) casts; or
  - new hematuria, as defined by a new, reproducible hematuria ( $\geq 11$  to 20 RBCs/hpf) or a reproducible increase in hematuria by 2 grades compared with baseline, associated with  $> 25\%$  dysmorphic RBCs, glomerular in origin, exclusive of menses, accompanied by either an 800 mg increase in 24-hour urinary protein levels or new RBC casts.

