15.3.8. SELENA SLE FLARES

Occurrence of SELENA SLE flares will be recorded on the eCRF.

A mild/moderate flare is defined to include any of the following:

- increase in SLEDAI \geq 3 points, relative to baseline
- new/worse skin, stomatitis, serositis, arthritis, or fever
- increased prednisone < 0.5 mg/kg/day
- added NSAID/hydroxychloroquine
- increase in PhGA ≥ 1.0 , relative to baseline

A severe flare is defined to include any of the following:

- increase in SLEDAI ≥ 12 points, relative to baseline
- new/worse CNS-SLE, vasculitis, nephritis, myositis, platelet count $< 60,000/\mu\text{L}$, hemolytic anemia with hemoglobin < 7 mg/dL, requiring doubling > 0.5 mg/kg/day prednisone
- hospitalization for SLE
- prednisone > 0.5 mg/kg/day
- new immunosuppressive increase in PhGA to > 2.5 , relative to baseline

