15.3.8.2. ANALYSIS

The analysis for incidence of flares will replicate that performed for SRI, and will be performed for each severity grade (mild/moderate and severe) and overall.

The flare-free survival function will be estimated by treatment group and for all active-treated subjects combined using Kaplan-Meier methodology, with 95% confidence intervals based on Greenwood's formula. These survival curves will be plotted. The KM estimates of quartiles for time to event with the corresponding 95% CIs will be provided for each treatment and for all active-treated subjects, when estimable, using Greenwood's formula.

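### As written, the SELENA mild/moderate flare criteria also catch every flare that is severe by SLEDAI and some that are severe by PhGA, and the prednisone items can leave exactly 0.5 mg/kg/day ungraded

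*Protocol*

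**What the plan says.** Protocol 6.2.2 lists separate criteria for the two SELENA grades. Mild/moderate includes "a change in SLEDAI $\geq 3$ points", "increased prednisone $< 0.5$ mg/kg/day", and a PhGA rise of at least 1.0 on a 0 to 3 scale. Severe includes a SLEDAI change above 12, prednisone above 0.5 mg/kg/day, and a PhGA that reaches more than 2.5.

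SAP 15.3.8 treats the items as alternatives: "A mild/moderate flare is defined to include any of the following". It keeps "increased prednisone < 0.5 mg/kg/day" and the severe item above 0.5, but gives the severe SLEDAI item as "increase in SLEDAI ≥ 12 points, relative to baseline". It omits the 0 to 3 scale from the PhGA items, although SAP 15.3.5 describes PhGA as a 0 to 100 mm visual analogue scale. Flares are entered on the eCRF. SAP 15.3.8.1 derives time to flare separately by severity, and under SAP 15.3.8.2 the incidence analysis "will be performed for each severity grade (mild/moderate and severe) and overall".

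Protocol 5.7.2 allows temporary steroid bursts with an inclusive limit: "The maximum dosage during a burst is up to 0.5 mg/kg prednisone, or equivalent, including any other steroids being given". No other steroid increase is allowed.

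**The concern.** Two grades that are analysed separately need boundaries that give each event one label. Here the SLEDAI items are nested, the PhGA items overlap in part, and the prednisone items can leave a gap at a value that the protocol itself sets as a limit. Neither document says which grade applies when both lists are met.

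The mild/moderate outputs are at stake. Under SAP 15.3.8.2 each grade gets the analysis used for SRI (percentages with confidence intervals, Fisher's exact test, relative risk, logistic regression on dose) and a Kaplan-Meier curve. If severe flares sit in the mild/moderate row, that row becomes a count of flares of almost any grade, and a reader who takes it as mild/moderate only will misread it.

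**Working it through.** The plan gives no flare rate, power or event count to reproduce; sample size rests on clinical judgment (protocol 8.1). The check is therefore of the boundaries.

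**SLEDAI.** The score is a sum of whole-number items (SAP 15.3.4), so integer rises can be enumerated. Mild/moderate is a rise of 3 or more in both documents. Severe is above 12 in the protocol and 12 or more in the SAP.

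| SLEDAI rise | Protocol 6.2.2 | SAP 15.3.8 |
|---|---|---|
| 3 to 11 | mild/moderate only | mild/moderate only |
| 12 | mild/moderate only | both grades |
| 13 or more | both grades | both grades |

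No SLEDAI rise is severe only. For example, 4 to 18 is +14, which is at least 3 and also above 12.

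**PhGA (0 to 3 scale; steps of 0.1 are my assumption).** Mild/moderate depends on the size of the rise and severe on the level reached.
- Rises ending at 2.6, 2.7, 2.8, 2.9 or 3.0 can start from 26, 27, 28, 29 or 30 lower values: 140 in all.
- Those that are also at least 1.0 number 17 + 18 + 19 + 20 + 21 = 95, and meet both grades (1.0 to 2.6 is +1.6).
- The other 140 − 95 = 45 are severe only (1.7 to 2.6 is +0.9). Every baseline above 2.0 gives severe only.

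These are counts of possible pairs, not expected frequencies.

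**Prednisone.** The stand-alone items are below 0.5 and above 0.5 mg/kg/day. Consider a burst to exactly 0.5:
- If below 0.5 means the resulting dose, 0.5 meets neither item.
- If it means the size of the increase, a burst to 0.5 from any nonzero baseline is an increase below 0.5 and counts as mild/moderate. At 60 kg, 10 to 30 mg/day is 20/60 = 0.333; at 80 kg, 10 to 40 mg/day is 30/80 = 0.375. Only a subject on no baseline steroid (30/60 = 0.500) falls in the gap.

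**How reachable exactly 0.5 is.** The documents do not say how often bursts reach the ceiling. Assume whole-kg weights from 50 to 100 kg (51 values) and dose steps of 5, 2.5 or 1 mg. Then half the weight is an exact multiple of the step at 6, 11 or 26 weights: 12%, 22% or 51%. With weights to 0.1 kg (501 values), the same 6, 11 and 26 give 1.2%, 2.2% and 5.2%.

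**Weight of one subject.** With 8 subjects planned per active dose and 8 on placebo, one subject is 1/8 = 12.5 percentage points.

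**The case against.** The strongest reply is that the grading may be settled elsewhere. Flares are recorded on the eCRF, and the form is not in the documents. If it takes one grade per flare, nothing is counted twice. This stands: double counting is a risk under the written criteria, not a demonstrated result. It does not remove the need for a rule, because about 20 sites would apply these criteria and the text gives no precedence.

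A second reply is that separate analyses by severity are a legitimate choice, since SAP 15.3.9.1 analyses a subject's moderate and severe BILAG flares separately. That is fair for a subject who has two events. It does not cover one SELENA event that meets both definitions.

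A reader might infer three stronger things that the documents do not support:
- *That the by-severity analysis cannot show an effect on severe flares.* Severe flares are analysed as their own grade. The overlap moves severe events into the mild/moderate row, never the reverse.
- *That all severe flares are counted twice.* One met only through hospitalization or a new immunosuppressive need not meet any mild/moderate item.
- *That flares treated at the burst ceiling are lost.* The items are alternatives, so new or worse skin disease, arthritis, serositis or fever, a SLEDAI rise of 3, or a PhGA rise of 1.0 still qualifies. SAP 15.1 uses the event date and falls back on the visit date only when none is recorded, so events between visits are foreseen.

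**Conclusion.** The criteria are wrong as written, with low impact. Every flare that is severe by SLEDAI, and some that are severe by PhGA, also meet the mild/moderate definition. A SLEDAI change of exactly 12 depends on which document is followed. Exactly 0.5 mg/kg/day is in neither stand-alone prednisone item on the resulting-dose reading, and on the increment reading only for subjects on no baseline steroid.

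The mild/moderate incidence row and its Kaplan-Meier curve can therefore include severe flares, subject to the unseen eCRF rule. The overlap does not change the severe or overall rows; the disagreement at 12 is a separate matter and can move an event into or out of the severe row. A ceiling-dose burst goes uncounted only if no other flare item is met. The percentages for reaching exactly 0.5 rest on assumed weights and dose steps and are not event rates.

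Impact is limited because protocol 6.2.3.3 places SELENA flares among its optional exploratory outcomes. They do not enter the Day 85 SRI endpoint, p-values are nominal, and the study's primary objective is safety and tolerability.

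**What to change.** Edit protocol 6.2.2 and SAP 15.3.8, for outcome classification only and with no change to any rescue rule:
1. Cap the mild/moderate SLEDAI and PhGA items below the severe cut-offs, or classify each flare by its worst grade only. Keep overall as either grade.
2. State whether the mild/moderate prednisone limit is a resulting dose or an increment, then assign the boundary value to one grade.
3. Reconcile the severe SLEDAI cut-off (above 12 in the protocol, 12 or more in the SAP).
4. State the PhGA cut-offs on the scale actually collected. If the 0 to 3 scale is simply stretched to 100 mm (an assumption), 1.0 becomes 1.0/3 × 100 = 33.3 mm and 2.5 becomes 2.5/3 × 100 = 83.3 mm; taken literally in millimetres, 1.0 would be 1 mm.

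Items 2 to 4 should be settled before the caps are written, because the caps depend on them. The eCRF instructions should match. The cost is a few lines of text and a small derivation change; no new data are needed.
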